Hospitalization for congestive heart failure reduces the patient's quality of life and represents a large monetary investment on the part of society. While improvement in ventricular function and symptom score would be expected to translate into shorter length of stay, an increase in frequency or duration of hospitalization during the period of drug titration might counteract a beneficial long term effect of this therapy. Thus frequency, duration, and cost of hospitalization as well as quality of life are important issues to examine.

We will examine prospectively whether left ventricular ejection fraction improves by 3 months and whether left ventricular function continues to improve between 3 and 12 months or deteriorates in the interim. Prior smaller trials have shown continued improvement between 3 and 6 months.^{28,35,58} We will also test the hypothesis that patients who respond to beta-blocker therapy (i.e. have an improvement in left ventricular ejection fraction) live longer. Precedent for such an examination comes from the results of the V-HeFT trial.⁶⁸ We will examine whether beta-adrenergic blocking agents reduce the incidence of myocardial infarction in patients with congestive heart failure as they have been shown to do in one study of post myocardial infarction secondary prevention (from 20.1% to 14.4%)⁶⁹. We will analyze the combined endpoint of transplant/mortality. In addition, we will compare the groups with respect to the need for changes in co-therapy.

D. Treatment interactions or effect modifiers

Analysis of all cause mortality will take into account the following variables that may modify

the association between treatment and mortality:

- 1. Presence or absence of coronary artery disease
- 2. Gender
- 3. Race
- 4. Age
- 5. Baseline left ventricular ejection fraction
- 6. Baseline serum sodium concentration
- 7. Baseline NYHA functional class
- 8. Baseline plasma norepinephrine
- 9. Baseline creatinine
- 10. Baseline heart rate
- 11. Baseline heart rhythm (sinus rhythm vs. atrial fibrillation)
- 12. Baseline systolic blood pressure
- 13. Improvement in left ventricular ejection fraction from baseline to 3 months
- 14. Change in creatinine and change in BUN/creatinine ratio from baseline to 3 months
- 15. VA versus non-VA site, after adjusting as far as possible for clinical prognosis

E. Justification of examining treatment interactions or effect modifiers

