The primary objective of this study is to determine whether treatment with beta-adrenergic blockade compared to placebo reduces all cause mortality in patients with moderate to severe congestive heart failure who are concurrently receiving optimal medical therapy. The null hypothesis to be tested is that there is no difference in survival time between active and placebo arms.

Two-tailed treatment comparisons will be made by the nonparametric logrank statistic with the exact variance calculation stratified by site, presence/absence of CAD and gender. This statistic is the optimal nonparametric test when censoring is equal in the treatment groups under proportional hazards. The analysis will include all survival times for all randomized patients in the treatment group to which the patient had originally been assigned (intention-to-treat principle). Significance levels will be set in accordance with the plan for monitoring the study.

Cumulative survival curves will be constructed by Kaplan-Meier methods.⁷⁹ The Cox life table regression method⁸⁰ will also be used to calculate estimates of relative risk, provided the model fits the data.

3. Secondary Objectives

Treatment differences will be evaluated in cause-specific cardiovascular mortality: total cardiovascular mortality, sudden death, worsening congestive heart failure, and ischemic cardiac events. These outcomes will be classified by the Mortality Committee which will remain blinded to treatment assignment. Cause-specific mortality will be further examined to estimate if treatment effect is similar for the different causes of death. Also, the cost of the two therapies will be examined.

The frequency of adverse effects in each treatment group will be analyzed using the chi-square statistic.

4. Subgroup analyses

All prior subgroup hypotheses related to treatment effect modification will be examined with tests to detect significant interactions. Our clinical interest focuses on qualitative interactions. We will use appropriate methods such as Cox regression⁸⁰ and stratified Kaplan-Meier curves.⁷⁹ However, the power to detect differences in treatment effects among subgroups will generally be lower than the power to detect an overall treatment effect. If tests of interaction are significant, then estimates of treatment effect will be derived within each subgroup. All reports of differences based on data-derived subgroups will be identified as such.

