The following subgroups will be included in analyses to evaluate the effect of beta-adrenergic blocking agents on all cause mortality

- 1. Presence or absence of coronary artery disease.
- 2. Gender
- 3. Race
- 4. Age
- 5. Baseline left ventricular ejection fraction.
- 6. Baseline serum sodium concentration.
- 7. Baseline NYHA functional class.
- 8. Baseline plasma norepinephrine.
- 9. Baseline heart rate.
- 10. Baseline heart rhythm (sinus rhythm versus atrial fibrillation).
- 11. Baseline systolic blood pressure.
- 12. Improvement in left ventricular ejection fraction from baseline to 3 months of therapy.
- 13. VA versus non-VA site, after adjusting as far as possible for clinical prognosis.

5. Other analyses

Additional analyses for treatment group effects will include as outcome variables:

- a. Hospitalizations per month of life
- b. Quality of life indicators

c. Incidence of myocardial infarction

d. Left ventricular ejection fraction at 3 and 12 months of therapy.

As beta-adrenergic blockade has been shown to improve ventricular function in patients with congestive heart failure, examination of changes in left ventricular ejection fraction in the bucindolol group will be compared to the placebo group. Analyses will include examination of the response of patients (i.e. change in left ventricular ejection fraction) with regard to baseline norepinephrine levels, baseline heart rate, baseline ejection fraction, baseline systolic pressure and presence or absence of coronary artery disease, to determine which group will have the most favorable hemodynamic response to beta-adrenergic blockade.

C. Interim analysis

Interim monitoring will focus on patient intake (overall and within hospital), hospital adherence to protocol, adverse reactions, baseline comparability of treatment groups and effect of treatment on the primary study outcome.

Due to ethical considerations, the study will be reviewed by the DSMB which may recommend early termination of the trial based on interim analyses. The DSMB will use a Lan-DeMets upper boundary with an intermediate spending function, and stochastic curtailment for the lower boundary.

IX. Data Collection and Management

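### Treatment effects should be reported for every prespecified baseline subgroup, with the interaction test limiting claims rather than deciding what is estimated

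*Protocol*

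**What the plan says.** Protocol section VIII.B.4 (Subgroup analyses) sets out a sequence. First, "All prior subgroup hypotheses related to treatment effect modification will be examined with tests to detect significant interactions". The type of effect modification sought is stated: "Our clinical interest focuses on qualitative interactions". The methods are left open: "We will use appropriate methods such as Cox regression", with stratified Kaplan-Meier curves as the second example. Then comes the reporting rule: "If tests of interaction are significant, then estimates of treatment effect will be derived within each subgroup".

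The section also warns that power is lower for subgroup differences than for the overall effect, and it promises to label data-derived subgroups. Its list of factors is introduced by "The following subgroups will be included in analyses to evaluate the effect" and ends at "13. VA versus non-VA site, after adjusting as far as possible for clinical prognosis". The list of effect modifiers in section IV.D ends at "15. VA versus non-VA site, after adjusting as far as possible for clinical prognosis"; it adds baseline creatinine and an item on 3-month changes in creatinine and in BUN/creatinine ratio.

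**The concern.** An interaction test can do two jobs. It can limit what is claimed about subgroups, which is a usual and sound guard. It can also decide which subgroup effects are estimated at all, and the sentence in VIII.B.4 gives it this second job. Estimates that appear because the data have already diverged overstate the divergence on average, and the sentence does not ask for estimates in the subgroups where the effect looked the same.

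There is also a mismatch of aim. The stated interest is in benefit in one group and harm in another, but the trigger is any significant interaction, including a mere difference in the size of benefit. None of the methods named is specific to qualitative interaction.

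Section IV.E says that the purpose is to find out which patients gain most in survival, and etiology, race, ejection fraction and gender are singled out in the objectives. A chance split reported with inflated estimates could be read as guidance on whom to treat. The primary analysis is not affected.

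**Working it through.** **1. The plan's own figure.** The protocol gives no figure for the subgroup tests. The anchor is the planned number of deaths, 916 (Appendix A, Table 1: 85% power, two-sided 5%, about 16% cumulative noncompliance). Appendix A, section B, item 5 gives an adjusted placebo mortality of 35% and an adjusted reduction of 15%.

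- Active-arm mortality: 0.35 × 0.85 = 0.2975.
- HR = ln(1 − 0.2975) / ln(1 − 0.35) = 0.3531 / 0.4308 = 0.820.
- Deaths by Schoenfeld's formula: 4 × (1.960 + 1.036)² / (ln 0.8197)² = 909. Freedman's formula gives 915.

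Both agree closely with 916, so an HR of 0.82 with 916 deaths represents the plan's design.

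**2. The rule when the effect is the same in everyone.** Assumptions: HR 0.82 in all patients, 1:1 allocation, two-level subgroups with D1 + D2 = 916 deaths, and 0.05 two-sided per interaction test. The protocol states 5% for the main test; it states no level for interactions. The 33% share is the target for women in section V.C; the 50% and 20% shares are assumed, to give a range.

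- SE of a subgroup log HR = 2/√D. SE of the difference = √(4/D1 + 4/D2).
- Average |Z| given |Z| > 1.96 is φ(1.96)/0.025 = 2.338.
- Average lower and higher log HR = ln 0.82 ∓ ½ × 2.338 × SE.
- Example at 50:50: SE = 0.132, so −0.198 ∓ 0.154, giving HRs of 0.70 and 0.96.

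| Split | SE | Smallest significant HR ratio | Average lower HR | Average higher HR | Opposite sides of 1 |
|---|---|---|---|---|---|
| 50:50 | 0.132 | 1.30 | 0.70 | 0.96 | 26% |
| 33:67 | 0.141 | 1.32 | 0.70 | 0.97 | 35% |
| 20:80 | 0.165 | 1.38 | 0.68 | 0.99 | 48% |

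The last column is from simulation (2,000,000 pairs per split) and is conditional on a chance-significant interaction.

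**3. The rule when there is a real interaction (50:50 split).**

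- True HR ratio 1.10: significant 11% of the time, then reported on average as about 1.38 (3.4-fold on the log scale).
- True ratio 1.25: significant 39% of the time, then about 1.42 (1.6-fold).
- True ratio 1.50: significant 87% of the time, then about 1.55 (1.08-fold).

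**4. Ordinary interaction test against a qualitative test (Gail-Simon, two subgroups, 50:50).**

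- True HRs 0.70 and 0.95 (both benefit): the ordinary test is significant in 64%, the qualitative test in 1.4%.
- True HRs 0.75 and 1.20 (opposite directions): 94% against 57%.

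A significant ordinary interaction therefore does not distinguish the two patterns.

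**5. What showing everything would cost (homogeneous HR 0.82).** Chance that a factor shows its two HRs on opposite sides of 1:

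- All estimates shown, 50:50: each subgroup SE is 2/√458 = 0.0935, and P(Z > 0.198/0.0935) = 0.017, so 2 × 0.017 × 0.983 = 3.3%.
- All estimates shown, 20:80: the subgroup SEs are 0.148 and 0.074, the two probabilities are 0.090 and 0.004, and the total is 9.3%.
- Under the present rule: 0.05 × 0.26 = 1.3% and 0.05 × 0.48 = 2.4%.

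**The case against.** The strongest defence is that gating on an interaction test protects readers. The figures in step 5 support it: with a homogeneous effect, showing every subgroup displays more point estimates above 1. Over 13 independent factors with the same split, the chance of at least one is 36% to 72%, against 16% to 27% under the rule. This stands as a cost. It does not rescue the rule, because the extra estimates are unselected and would come with their confidence intervals and the interaction result, whereas the gated ones are shown because they diverged.

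The protocol's safeguards also deserve credit: the factors are prespecified, low power is acknowledged, and data-derived subgroups are to be labelled. None of these removes selection among the prespecified subgroups.

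A reader might infer four stronger points that the text does not support.

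- That estimates will appear solely after a significant test and the rest will be withheld. This goes beyond the wording. The sentence does not forbid other estimates, and the Kaplan-Meier curves and the list of subgroups carry no significance condition. The conditional reading is the natural one, not the literal one.
- That the tests are unadjusted, with a 49% (13 tests) to 54% (15 tests) chance of a false signal. That rests on silence, an assumed 0.05 per test and independence; at a correlation of 0.5 it is 33% to 36%. The level and any multiplicity rule can sit in a statistical analysis plan, so their absence is no part of this point.
- That qualitative interaction will not be tested. The methods are given as examples, so the list is open, and nothing says that a qualitative claim will rest on the Cox p-value.
- That any reported split will be badly exaggerated. Step 3 shows that this depends on the true interaction.

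**Conclusion.** The point holds as a cheap improvement to the analysis wording. The protocol states a rule that, read naturally, conditions subgroup estimation on divergence. If there is no true interaction, the estimates it calls for would average 0.70 and 0.96 to 0.68 and 0.99 around a common HR of 0.82. They would point in opposite directions in 26% to 48% of chance-significant splits. The distortion is large for small true interactions and minor for large ones.

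These sizes rest on 916 deaths, two-level subgroups, shares of 20% to 50% and 0.05 per test. The direction of the bias does not depend on those choices. On qualitative interaction, the supportable statement is that no named method is specific to it and that the ordinary interaction test cannot establish it alone.

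**What to change.** Replace the conditional sentence in VIII.B.4 with wording to this effect: for every level of every prespecified baseline subgroup, the treatment effect and its 95% CI will be reported whatever the interaction p-value, together with the interaction estimate and the number of interaction tests done; the interaction test will limit the claims made, not decide what is estimated; and a claim of qualitative interaction will not rest on the ordinary Cox interaction p-value alone. A test aimed at that hypothesis, such as Gail-Simon, is one option. To state the number of tests, the lists in IV.D and VIII.B.4 need to be brought into line.

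The cost is a change of wording and one forest plot, with no effect on conduct, sample size or the primary test. The downside is that more subgroups will show an HR above 1 by chance, so the text should say that they are to be read with their CIs and the interaction result. A qualitative test also has less power (57% in the example above), so fewer such claims will be possible.

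### Three-month changes in LVEF and renal function are listed as treatment-effect modifiers, so treatment comparisons within those groups would be non-randomised and open to bias

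*Protocol*

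**What the plan says.** VIII.B.4 introduces its list with "The following subgroups will be included in analyses to evaluate the effect of beta-adrenergic blocking agents on all cause mortality". Item 12 of that list is "Improvement in left ventricular ejection fraction from baseline to 3 months of therapy"; the other entries are baseline characteristics or site type.

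IV.D, the list of variables that may modify the link between treatment and mortality, has the same LVEF entry as item 13 ("Improvement in left ventricular ejection fraction from baseline to 3 months"). Item 14 is "Change in creatinine and change in BUN/creatinine ratio from baseline to 3 months". The renal changes, and baseline creatinine (item 9), are in IV.D but not in VIII.B.4.

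VIII.B.4 fixes the method: "All prior subgroup hypotheses related to treatment effect modification will be examined with tests to detect significant interactions". It then adds: "If tests of interaction are significant, then estimates of treatment effect will be derived within each subgroup".

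Other sections bear on the same variables. IV.C says: "We will also test the hypothesis that patients who respond to beta-blocker therapy (i.e. have an improvement in left ventricular ejection fraction) live longer". VIII.B.5 opens its LVEF comparison with "As beta-adrenergic blockade has been shown to improve ventricular function in patients with congestive heart failure". IV.E cites earlier Veterans Affairs heart failure trials in which larger ejection fraction gains went with better survival whatever the assigned treatment. It also reads a rising BUN/creatinine ratio as a likely sign of worsening on active drug.

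**The concern.** A treatment-effect subgroup keeps the protection of randomisation only if membership is settled before treatment can influence it. Change in LVEF at 3 months is partly a result of treatment, and by the protocol's own account it also tracks prognosis. A placebo patient who improves has improved spontaneously. Bucindolol patients who improve include some who would not have improved without the drug. Improvers in the two arms therefore differ in underlying prognosis, and so do non-improvers. The renal changes raise the same problem to the extent that treatment affects them.

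A further difficulty is that patients who die before the 3-month visit have no value and belong to neither group.

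What is at stake is the secondary message of the trial: which patients appear to benefit, and whether response to the drug is credited with survival that it did not cause.

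**Working it through.** **1. The plan's own figure.** Appendix A gives 2790 patients (rounded to 2800) and 916 deaths for 85% power. Its inputs are two-sided 5%, annual mortality 15% against 11.25%, a 3-month lag, 3 years of uniform accrual in a 4.5-year trial, 1% annual loss, noncompliance of 10% then 2% per year, and transplant rates of 1.85% and 0.37% from year 2 with 80% of recipients otherwise dying. A Lakatos-type calculation, with noncompliers moved to the transplant-adjusted placebo rate, gives 2779 patients, 913 deaths and 85.3% power at 2800. The design figures reproduce, so 916 is a fair denominator.

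**2. Deaths before the 3-month measurement.** The assumed lag gives both arms the placebo rate over this period.

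- Risk by 3 months = 1 − (1 − 0.15)^0.25 = 0.0398.
- Expected deaths = 2800 × 0.0398 ≈ 111.
- Share of planned deaths = 111 / 916 ≈ 12%.
- At 10% annual mortality the count is about 73; at 20% it is about 152.

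**3. Bias within groups, counting survival from month 3.** The documents give no value for the drug's shift in LVEF change, for its correlation with prognosis or for a cut-off defining improvement, so these are assumptions. Large simulated cohorts with *no* true effect modification were fitted by Cox regression.

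| Assumed setting | True HR | HR within improvers and within non-improvers |
|---|---|---|
| Drug shifts LVEF change 0.5 SD; correlation 0.5 with prognosis | 1.00 | about 1.04 to 1.10 in both |
| Same | 0.82 | about 0.87 to 0.92 in both |
| Drug adds 3 or 5 LVEF units; improver = rise of at least 5; prognostic log-hazard slope 0.3 or 0.6 per SD | 1.00 | 1.05 to 1.20 in both |
| Same | 0.75 | 0.79 to 0.90 in both |
| 0.5 SD shift, no shared prognostic factor | 1.00 or 0.82 | close to the true value |

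Where the true HR is 1.00, the landmark comparison without the split returns about 1.00, so the shift comes from the split. For scale, an HR of 0.90 when the truth is 0.82 keeps ln 0.90 / ln 0.82 = 0.105 / 0.198 ≈ 53% of the log effect.

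**4. Would the interaction test pass such results through?** Both groups shift in the same direction, so the ratio of their HRs stays near 1 (about 0.97 to 1.04).

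- Deaths after month 3: 916 − 111 = 805, say 400 per group.
- SE of each log HR ≈ √(4/400) = 0.10; SE of their difference ≈ √(0.01 + 0.01) = 0.14.
- A ratio of 1.04 gives z = 0.039 / 0.14 ≈ 0.28; a ratio of 0.97 gives z ≈ 0.2.

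The test then rejects in about 5 to 6% of trials, close to its nominal 5%.

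**5. If early deaths were counted as non-improvers.** Early deaths are equal in the two arms, but the bucindolol non-improver group is smaller because the drug moves patients out of it. Its death rate is therefore inflated more. With a true HR of 0.82 and no effect modification, one such run gives 0.83 in improvers and 0.96 in non-improvers. Under the 0.5 SD setting, with a prognostic slope of 0 or 0.5 per SD, the interaction test rejects in roughly 12 to 25% of trials instead of 5%.

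**The case against.** A reader might infer that the plan, followed as written, will report harm or lost benefit in both response groups. The documents do not support that. Estimates within subgroups follow only a significant interaction, and step 4 shows that the landmark bias seldom produces one. Even if an HR of 1.09 were reported on 400 deaths, its 95% interval would be 1.09 × exp(±1.96 × 0.10), about 0.90 to 1.33, which is no clear finding of harm.

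A reader might also infer that immortal-time bias is built in. It is not: the protocol does not say how early deaths are classified or when follow-up starts for these analyses, and such detail may sit in an analysis plan that is not shown. Step 5 is a conditional result.

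Three further points stand. IV.E describes the LVEF analysis as relating LVEF change, treatment and survival, which is a legitimate exploratory aim. The sizes in step 3 rest on assumed parameters. VIII.B.4 itself contains only the LVEF item; the renal changes reach the interaction tests through its reference to all prior hypotheses.

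The classification remains. Placing post-randomisation changes in the lists of treatment-effect modifiers, with treatment estimates within subgroups as the declared next step, is a stated choice and not a detail left open. A landmark added elsewhere would settle the early deaths but would not make the groups comparable between arms.

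**Conclusion.** The point holds as a should-fix. Treatment comparisons within groups defined by 3-month change in LVEF, creatinine or BUN/creatinine are not randomised comparisons and are open to bias. For LVEF, the protocol itself supplies both conditions for it: treatment moves the variable, and the variable tracks survival. For the renal changes the effect of treatment is suggested in IV.E and less firmly stated.

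Under a 0.5 SD drug shift and correlation 0.5 with prognosis, a true HR of 1.00 appears as about 1.04 to 1.10 in both groups. Stronger assumptions reach 1.20. With no shared prognostic factor, a landmark analysis shows little bias. About 111 patients, 12% of planned deaths, would have no 3-month value at 15% annual mortality. Counting them as non-improvers could create a spurious interaction and open the significance gate.

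The primary logrank test, the sample size and the baseline subgroups are unaffected.

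**What to change.** - Remove item 12 from VIII.B.4 and items 13 and 14 from IV.D as treatment-effect modifiers.
- Carry one identical list in both sections, without post-randomisation variables and including baseline creatinine.
- Analyse the 3-month changes as exploratory landmark analyses: patients alive with a 3-month value, survival counted from month 3, arm and change both in the model. Label them prognostic and non-randomised.
- Report deaths and missing values before 3 months by arm.
- Report no treatment effects within response groups.

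The cost is a change of wording, a small amount of extra analysis and slightly fewer events in the landmark analyses. No new data are needed.
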